- (3) young people with low risk on an EC profile *CBT self-help* will outperform *usual practice and self-monitoring* in
 - increasing mental well-being at 3 months (3a; primary outcome; WEMWBS);
 - increasing social and occupational/academic functioning (WSAS), quality of life (EQ5DL), at 3 months (3b) (secondary outcomes)
 - reducing symptoms of depression (PHQ-9) and anxiety (GAD-7) at 3 months (3c; secondary outcomes as general indices of poor mental health)

Secondary objectives will be: (1) to assess the effects of the intervention on primary and secondary outcomes over long-term (12-months follow up) and (2) at all time points (1, 3 and 12 months). The same hypothetical structure as above will be used.

Demographic information

Demographic information will be collected at baseline including participant age, sex, country of birth, country where currently reside, ethnic group, educational level, occupation, and parent's occupation. Occupational status of participant and their parent(s) will be used as an index of socio-economic status.

ECoWeB- PREVENT Trial

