## 6.3 Analysis methods

All continuous outcomes will be reported descriptively (mean, SD) at all follow-up timepoints. Inferential analyses The primary analyses for the primary and continuous secondary outcomes will use linear regression models with adjustment for baseline score, age (as a continuous variable rather than the dichotomised minimisation variable), country, and any other participant characteristics observed at baseline to be unbalanced across treatment arms (meeting the criteria set out in Section 5.5). The primary follow-up time will be at 3 months; analysis of 12-month follow-up data will also be performed using the same approach. The primary analyses will be based on an intention to treat (ITT) approach (i.e. all participants will be included in the analyses according to their randomised allocation) and will use observed data only.

As a secondary analysis, we will perform repeated measures analyses (using a mixed effects linear regression model with a random effect on participant) for primary and secondary continuous outcomes, including data from participants with observed data for at least one of the three follow-up timepoints. Analyses will be performed to compare both active interventions with usual care, and to compare the personalised active intervention with the standard active intervention. A fixed effect interaction between timepoint and trial arm will be used to evaluate differential treatment effects across timepoints. Adjustments for baseline covariates will be made as for the primary analysis regression models; baseline score will be included as a covariate. Binary outcome measures will be analysed using logistic regression models with adjustments for covariates as above.

The primary analyses will use only the data collected during the time window. The amount of such data will be determined, with the possibility of performing a sensitivity analysis should the amount of data collected outside the time window be substantive. These analyses will be performed using observed data for the ITT population (i.e. according to initial random allocation). No formal adjustments of p-values for multiple testing will be performed; the results for the primary outcome will be interpreted first and the results of the secondary outcomes will then be interpreted in the light of multiple testing. The results of all descriptive and inferential analyses for the primary and secondary continuous outcomes are set out in Tables A.4–A.10.

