#### 7. General analysis considerations

#### 7.1 Timing of analyses

The first set of statistical analyses will be performed when the 3-month outcome data is available and the database has been locked. At this point, the statistician will perform the 3-month inferential analyses (as well as descriptive analyses for 1- and 3-month data), whilst being unaware of treatment arm allocation. These analyses will be performed on the ITT population using observed data only. Following presentation of the results with anonymised allocations, the allocations will be revealed for interpretation of the results. Following revelation of treatment allocations, the remaining analyses of 3-month outcome data will be performed. Following completion of 12-month data collection and database lock, the remaining analyses of the 12-month outcome data will be performed. At this point the repeated measures analyses and analyses including imputed and observed data will be performed.

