## 8.11 Measurement of outcomes

The EQ-5D-3L will be administered with the adapted ADSUS at baseline, 3 and 12-months

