| Repeated       | l measures ana    | lyses (interact | ion between i  | ntervention | arm (usual car | e as reference) a | nd timepoint (1- | -month follow-up as | reference))       |   |
| Interactio     | on coefficient (9 | 95% confidenc   | e interval)    |             |                |                   |                  |                     |                   |   |
|                |                   | 3-n             | nonth follow-u | ıp          |                |                   | 12-n             | nonth follow-up     |                   |   |
|                | Personalised      | digital self-he | lp + Non-p     | ersonalised | digital self-  | Personalised d    | igital self-help | Non-personalised    | digital self-help | ) |
|                | usual care        | -               | help +         | usual care  | -              | + usual care      |                  | +usual care         |                   |   |
| ITT            |                   |                 |                |             |                |                   |                  |                     |                   |   |
| observe        |                   |                 |                |             |                |                   |                  |                     |                   |   |
|                |                   |                 |                |             |                |                   |                  |                     |                   |   |
| d data         |                   |                 |                |             |                |                   |                  |                     |                   |   |
| d data
only |                   |                 |                |             |                |                   |                  |                     |                   |   |
|                | Global p-valu     | e               |                |             |                |                   |                  |                     |                   |   |
|                | Global p-valu     | e               |                |             |                |                   |                  |                     |                   |   |
|                | Global p-valu     | e               |                |             |                |                   |                  |                     |                   |   |

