| ITT,
observe
d data
only               |  |   |                        |  |   |                        |             |  |   |                                |  |   |                                |
| CACE,
observe
d data
only              |  |   |                        |  |   |                        |             |  |   |                                |  |   |                                |

Table A.8 EQ5D-3L at baseline, 1-, 3- and 12-month follow-up

| ITT,       |  |                |          |                |  |          |               |                 |         |                  |                   |   |
|------------|--|----------------|----------|----------------|--|----------|---------------|-----------------|---------|------------------|-------------------|---|
| observe    |  |                |          |                |  |          |               |                 |         |                  |                   |   |
| d and      |  |                |          |                |  |          |               |                 |         |                  |                   |   |
| imputed    |  |                |          |                |  |          |               |                 |         |                  |                   |   |
| data       |  |                |          |                |  |          |               |                 |         |                  |                   |   |
| Repeated   | measures ana                                   | lyses (interac | tion bet | ween interven  | tion arm (usual c                            | are as i | reference) an | d timepoint (1- | -month  | n follow-up as r | eference))        |   |
| Interactio | n coefficient (                                | 95% confiden   | ce inter | val)           |  |          |               |                 |         |                  |                   |   |
|            |  | 3-             | month f  | ollow-up       |  |          |               | 12-n            | nonth f | follow-up        |                   |   |
|            | Personalised digital self-help +
usual care |                |          | Non-personal   | ised digital self-                           | Ре       | rsonalised di | gital self-help | Non     | -personalised c  | ligital self-help | ) |

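### The repeated-measures tables print only arm-by-time interactions against a 1-month reference, so they omit the promised arm contrasts at each visit, and EQ-5D has no 1-month visit to refer to

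*SAP*

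**What the plan says.** In protocol 3.1, both trials have a secondary objective to assess intervention effects "at all time points (1, 3 and 12 months", using the same three pairwise hypotheses as at 3 months. Protocol 10.3.3 (item 2) assigns this to a repeated-measures analysis of everyone with at least one follow-up.

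SAP 6.3 specifies a mixed linear model with a participant random effect and says: "Analyses will be performed to compare both active interventions with usual care, and to compare the personalised active intervention with the standard active intervention". The next sentence gives the only treatment term it describes: "A fixed effect interaction between timepoint and trial arm will be used to evaluate differential treatment effects across timepoints". On reporting it says: "The results of all descriptive and inferential analyses for the primary and secondary continuous outcomes are set out in Tables A.4–A.10".

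Each of those tables (SAP section 11) has three parts:

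- Means, SDs and n by arm at baseline, 1, 3 and 12 months.
- Between-group differences with 95% CIs at 3 and 12 months for all three arm pairs.
- A repeated-measures block of interaction coefficients with 95% CIs for each active arm at 3 and at 12 months, with usual care and 1 month as references, plus a global p-value.

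At the first analysis, SAP 7.1 plans 3-month inference "as well as descriptive analyses for 1- and 3-month data".

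For EQ-5D, SAP 8.11 says: "The EQ-5D-3L will be administered with the adapted ADSUS at baseline, 3 and 12-months". The appendix nevertheless has "Table A.8 EQ5D-3L at baseline, 1-, 3- and 12-month follow-up", with the same 1-month reference in its repeated-measures block. Table A.9 (EQ5D Health State) is laid out the same way.

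**The concern.** An interaction against 1 month answers whether the treatment effect changed after 1 month. The stated objective asks how large the effect is at each visit. A statistician who fills in the shells as drawn answers the first question and leaves the second without an answer from the planned model.

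Three things are lost:

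- **The 1-month effect.** It is the arm coefficient at the reference visit, and the shells have no cell for it. SAP 6.9 expects most of the therapeutic effect in the first 4 weeks.
- **The mixed-model effects at 3 and 12 months.** This model uses participants seen at any follow-up. The 3-month regression uses only those observed at 3 months, with 40% attrition allowed for. The mixed-model estimate would therefore be a useful check on the primary result.
- **Personalised versus standard.** SAP 6.3 promises this pair, but the block has no cell for it.

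SAP 4.1 tells readers to interpret individual contrasts from their 95% CIs. In this block those intervals describe changes in effect, not effects. For EQ-5D the problem is more basic, because the reference visit has no data.

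**Working it through.** **Inputs.** The model and reference levels come from SAP 6.3 and the shells of Tables A.4 to A.10. The illustrative effect is the WEMWBS minimum important difference of 3.0 points (SD 11.3) from SAP 3.4. The plan's own sample size reproduces: 2 × (1.960 + 1.282)² × 11.3² / 3.0² = 298.2, so 299 per arm against the stated 300, and 300 / 0.6 = 500 after attrition. It is not disputed and nothing below depends on it.

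**What the coefficients mean.** Write effect(a, t) for active arm *a* minus usual care at visit *t*. With usual care and 1 month as references:

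- arm coefficient = effect(a, 1)
- interaction at *t* = effect(a, t) − effect(a, 1)

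Three arms and three visits give two arm coefficients and 2 × 2 = 4 interactions. The shells print the four interactions and not the two arm coefficients, so no effect at any visit can be recovered from the block.

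**Numbers put in**, solving the saturated arm-by-time model for set patterns:

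| True effect at 1, 3, 12 months | Arm coefficient (not printed) | Interaction at 3 | Interaction at 12 |
|---|---|---|---|
| 3, 3, 3 (constant) | 3 | 0 | 0 |
| 0, 0, 0 (none) | 0 | 0 | 0 |
| 3, 3, 0 (fades) | 3 | 0 | −3 |
| 0, 3, 3 (late) | 0 | 3 | 3 |

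The first two rows print identically. The third row, a benefit through 3 months that then disappears, prints as a 12-month deficit.

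**Personalised versus standard.** Subtracting the two arms' printed interactions gives the change in this contrast since 1 month as a point estimate. It gives no CI, because the covariance is not shown, and it never gives the contrast itself.

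**EQ-5D.** SAP 8.11 lists baseline, 3 and 12 months. The EQ-5D-3L row of the protocol's schedule (section 3.7) is marked at the same three times, with the 4-week cell empty. With no 1-month data, effect(a, 1) is undefined, so all four interactions in Table A.8 are inestimable, as are the four in Table A.9 if the health-state item is collected with the rest of the instrument. Only 12 versus 3 months can be estimated, which is one interaction per active arm.

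**The case against.** The interaction sentence is not an error: it states what an interaction measures, and the sentence before it plans the very comparisons said to be missing. The shells label the block as interaction coefficients with stated references. The primary time point is 3 months, protocol 3.5 names 12 months as the secondary endpoint, and the numbered hypotheses all concern 3 months. The 4-week remark in SAP 6.9 was written to grade app-outage disruption, not to set an endpoint. All of this stands, and it limits how much the point matters.

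A reader might infer that a stable benefit would vanish from the trial report. It would not: the regression block of the same tables gives 3- and 12-month differences for all three pairs, and the constant benefit would appear there as about 3 and 3. A reader might also infer that 1-month results go unreported, but means, SDs and n by arm are tabulated. What is absent is an estimated difference with its interval.

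The objection does not close the gap. SAP 6.3 names these tables as the place for all inferential results, and they have no cell for the 1-month contrast or for any mixed-model contrast at a visit.

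On EQ-5D, protocol section 4 says the same outcome measures are obtained at every assessment, which would include 1 month. The schedule and SAP 8.11 are more specific and agree with each other. The general statement is a conflict to reconcile, not a rescue of the shell.

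**Conclusion.** The point holds as a mismatch between the promised comparisons and the specified output of a secondary analysis. If the shells are followed, the objective of effects at 1, 3 and 12 months has no inferential answer at 1 month, no mixed-model arm contrast at any visit, and no personalised-versus-standard contrast from that model. The planned EQ-5D interactions, four per table in Tables A.8 and A.9, cannot be estimated.

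No primary conclusion is affected. It would also be wrong to put a size on the harm by saying that the interaction test rejects only 5% of the time under a constant benefit: that merely restates the nominal size of a test under its own null. Nor do the documents support saying that no EQ-5D mixed model can be fitted, since one can be fitted to 3 and 12 months.

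The conclusion assumes that the shells define the output, as SAP 6.3 says, and that EQ-5D, including its health-state item, follows SAP 8.11. It depends on no sample-size or alpha figure. It should be corrected, because the remedy is specific and nearly free.

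**What to change.** 1. In the repeated-measures block of Tables A.4 to A.7 and A.10, report from the same mixed model the three adjusted arm contrasts (personalised vs usual care, standard vs usual care, personalised vs standard) with 95% CIs at 1, 3 and 12 months: 3 × 3 = 9 estimates per outcome. Say so in SAP 6.3.
2. Keep the arm-by-time interaction test as a supplementary line, labelled as a test of change in effect. A joint test of all arm and arm-by-time terms is optional.
3. In Tables A.8 and A.9, remove the 1-month columns, fit the model to 3 and 12 months with 3 months as reference, and report 3 × 2 = 6 contrasts.
4. Reconcile protocol section 4 with the protocol schedule and SAP 8.11 on whether EQ-5D-3L is collected at 1 month.

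The cost is revised shells, a sentence or two in SAP 6.3, and one post-estimation command per model. It needs no new data and no change to the primary analysis.

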#### 6.4 Interactions between treatment and participant characteristics

To investigate differential treatment effects across subgroups of participants, we will perform a series of models, for the primary outcome only at 3-and 12-month follow-up, including an interaction term between treatment arm and the participant characteristic (as well as the other covariates to be adjusted for; each model will include one interaction term only). The participant characteristics to be investigated for differential treatment effects are age (continuous and dichotomised as for the minimisation algorithm), country and gender. The interaction terms will be reported as coefficients and 95% confidence intervals, with a global p-value (Table A.11). It is acknowledged that these analyses will have limited statistical power, and hence are exploratory in nature, and the results should be viewed with caution.

#### 6.5 Missing data

Demographic characteristics of participants who do not provide data for the primary outcome measure of their trial at 3- and 12-month follow-up will be set out (including participants who have

formally withdrawn (but allowed their previously collected data to be used), and participants not formally withdrawn but did not complete the primary outcome at follow-up) (Tables A.12 and A.13).

Multiple imputation using chained equations (MICE) will be used to impute primary and secondary continuous outcomes. Predictive mean matching will be the method for imputing individual scores; the number of imputed datasets will be determined by the percentage of participants in each trial that have missing 3-month outcome data (i.e. WEMWBS for PREVENT, PHQ-9 for PROMOTE). Imputation models will be informed by treatment arm, baseline scores, other covariates to be included in the model (i.e. minimisation covariates), and other baseline characteristics found to predict outcome or propensity for missingness (logistic regression models will be used to investigate the associations between baseline characteristics and missingness). Regression models using the imputed datasets will be performed using the same methods as described in Section 6.3 for the ITT population (Tables A.4–A.10). Analyses using imputed data will be considered as a secondary analysis.

## 6.6 Differential adherence analysis

Differential adherence within the active treatment arms is anticipated, which could impact the outcomes. Ideally, we wish to compare participants who adhere to their intervention with those in the comparator arm who would also have adhered to the treatment had they been allocated to it. To address this issue we will undertake a complier average causal effect (CACE) model, using a 2-stage least squares instrumental variable regression model. Such models will be performed for the continuous primary and secondary outcomes at 3- and 12-month follow-up using observed data only, and will include the covariates adjusted for in the linear regression models (Tables A.4–A.10). The CACE analyses will be considered as secondary analyses. The definition of a 'complier' will be: (i) complete at least one Challenge (some psychoeducation) and at least four Challenges completed or ten Tools used (to capture practice) OR (ii) (to capture combined usage) at least ten Challenges or Tools completed (any combination), including at least one Challenge and one Tool. (The definition of a 'complier' may be subject to further revision.)

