. Hypotheses

(1) Young people with high risk on an EC profile *personalised EC self-help* will outperform *digital CBT self-help* in

- reducing symptoms of depression at 3 months (1a; primary outcome, as index of poor mental health; PHQ-9);
- reducing symptoms of anxiety at 3 months (1b); (secondary outcome, as index of poor mental health; GAD-7)
- increasing mental well-being (WEMWBS), social and occupational/academic functioning (WSAS), quality of life (EQ5DL) at 3 months (1c). (secondary outcome).

(2) Young people with high risk on an EC profile personalised EC self-help will outperform usual practice and self-monitoring in

- reducing symptoms of depression at 3 months (2a; primary outcome, as index of poor mental health; PHQ-9);
- reducing symptoms of anxiety at 3 months (2b) (secondary outcome, as index of poor mental health; GAD-7);
- increasing mental well-being (WEMWBS), social, occupational/academic functioning (WSAS), quality of life (EQ5DL) at 3 months (2c) (secondary outcome).

(3) Young people with high risk on an EC profile the digital CBT self-help will outperform usual practice and self-monitoring in

- reducing symptoms of depression at 3 months (3a; primary outcome; as index of poor mental health; PHQ-9);
- reducing symptoms of anxiety at 3 months (3b; as index of poor mental health; GAD-7);
- increasing mental well-being (WEMWBS), social and occupational/academic functioning (WSAS), quality of life (EQ5DL) at 3 months (3c).

Secondary objectives will be: (1) to assess the effects of the intervention on primary and secondary outcomes over long-term (12-months follow up) and (2) at all time points (1, 3 and 12 months) The same hypothetical structure as above will be used.

Additional secondary outcome measures will assess anxiety, mental well-being, social functioning, quality of life, and educational achievement (see Table 15).

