## 3. Study methods

#### 3.1 Trial design

Both PROMOTE and PREVENT are 3-arm parallel group trials, with individual randomisation in a 1:1:1 ratio. For both trials, an external pilot will be carried out to identify any issues in the administrative aspects of the trial, such as participant recruitment, consent procedures for under 18s (in countries where parental consent is required for trial participation of under-18s. The data from this pilot will not be combined with the results of the main trials, which are fully powered definitive trials. Furthermore, the external pilot has no stopping criteria that would, if fulfilled, lead to the main trial being cancelled prior to commencement.

The usual care intervention comprises only self-monitoring using the app. The personalised active intervention consists of usual care plus two out of four modules for emotional competence self-help training, selected for each participant. The standard active intervention consists of usual care plus a self-help intervention based on CBT principles, also delivered via the app.

The ECoWeB trials will be performed within the framework of a cohort multiple RCT (cmRCT). A top level cohort of potential participants, whose eligibility for either PROMOTE or PREVENT has been established, will be recruited. These participants will consent to participating in the cohort and to being offered potential treatments if applicable via the screening website. Based on their baseline scores on eight measures (collected at baseline), to be converted to z-scores (using means and standard deviations derived from a validation study across all four sites), the participant will be allocated to either PROMOTE (lower risk of mental health problems) or PREVENT (higher risk of mental health problems). Full details of the process for allocation of participants to either PROMOTE

or PREVENT are reported elsewhere (Trial selection, randomisation, selection of emotional competence intervention components document).

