## 4. Statistical principles

### 4.1 Confidence intervals and p-values

All inferential analyses will be reported using 95% confidence intervals and p-values, with the threshold for statistical significance set at 0.05. No formal testing for multiple comparisons will be performed (whether for the multiple comparisons across the three trial arms or for multiple comparisons across the primary and secondary outcomes); the p-values for the primary outcomes will be interpreted first, and the p-values for the secondary outcomes will be interpreted in the light of the overall results. Global p-values will be used where there are two or more contrasts being examined in the same model; 95% confidence intervals will be used to interpret individual contrasts.

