#### 4.2 Intervention adherence and protocol deviations

For participants receiving the active interventions, we will descriptively report data on intervention adherence. Protocol deviations will be reported narratively within the trial report, with descriptive analysis only if required. With regard to treatment allocation, there is no possibility of a participant accessing one of the other active interventions, i.e. other than the allocated intervention.

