|   | Personalise
d digital
self-help +
usual care
vs. Usual
care | Non-
personalis
ed digital
self-help
vs. Usual
care    | self-help
care vs No |  | Global p-v  | r alue          | digi
hel | sonalised
ital self-
p + usual
e vs. Usual
e             | Non-
personalise
d digital
self-help
vs. Usual
care    | digital
usual
persoi     | nalised
self-help +
care vs Non-
nalised
self-help | Global p-valu   | IE                             |
| ITT,
observe
d data
only               |  |   |                         |  |   |                        |             |  |   |                                |  |   |                                |
| CACE,
observe
d data
only              |  |   |                         |  |   |                        |             |  |   |                                |  |   |                                |

| ITT,       |                  |                 |          |                |                    |         |               |                 |         |                |                   |   |
|------------|------------------|-----------------|----------|----------------|--------------------|---------|---------------|-----------------|---------|----------------|-------------------|---|
| observe    |                  |                 |          |                |                    |         |               |                 |         |                |                   |   |
| d and      |                  |                 |          |                |                    |         |               |                 |         |                |                   |   |
| imputed    |                  |                 |          |                |                    |         |               |                 |         |                |                   |   |
| data       |                  |                 |          |                |                    |         |               |                 |         |                |                   |   |
| Repeated   | l measures ana   | lyses (interac  | tion bet | ween intervent | tion arm (usual ca | re as r | eference) an  | d timepoint (1- | -month  | follow-up as r | eference))        |   |

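### Does SAP 6.6 need amending because it does not name the exposure for the personalised-versus-CBT complier analysis?

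*SAP*

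**What the plan says.** SAP 6.6, repeated in Protocol 10.3.3, anticipates differential adherence in the active arms and states that "we will undertake a complier average causal effect (CACE) model, using a 2-stage least squares instrumental variable regression model". The comparison it wants is between adherers and "those in the comparator arm who would also have adhered to the treatment had they been allocated to it". A complier is defined by a threshold of Challenges completed and Tools used, worded the same for both apps and open to later revision. The analysis is labelled secondary, and SAP 6.9 limits it to participants whose app use was not disrupted before 3 months.

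The shells for Tables A.4 to A.10 set a CACE row against three contrasts: EC versus usual care, CBT versus usual care, and EC versus CBT. A global p-value column follows. On that column SAP 4.1 says "Global p-values will be used where there are two or more contrasts being examined in the same model".

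On access, SAP 4.2 says "there is no possibility of a participant accessing one of the other active interventions" and SAP 3.1 says "The usual care intervention comprises only self-monitoring using the app". The exposure is therefore clear for each app against usual care: compliance with that app, and zero in usual care. For EC versus CBT, neither document names the exposure or states the identifying assumption.

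**The concern.** Both arms of the EC-versus-CBT contrast have an app with Challenges and Tools, so the complier rule can be met in either. Two codings suggest themselves, and each has a weakness.

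- **Compliance with the EC app, zero in the CBT arm.** The stated target and the lack of crossover point this way. Two-stage least squares then assigns the whole EC-minus-CBT difference to EC compliers, so EC non-compliers must have the same mean outcome under either app. That sits uneasily with hypothesis 3 in Protocol 3.1, which for PREVENT reads "the digital CBT self-help will outperform usual practice and self-monitoring in" reducing depressive symptoms. If CBT works, and some people would comply with CBT but not EC, the estimate is pulled against EC.
- **One flag for complying with one's own app.** The first stage is then the difference in compliance between the arms, which may be close to zero.

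The contrast is hypothesis 1 in both trials, and the cell would be printed below the intention-to-treat result. A distorted complier estimate there could be misread, and the three CACE cells might not add up.

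**Working it through.** **Scale.** SAP 6.6 gives no figure to reproduce. The PROMOTE sample size supplies the scale: 2 × (1.960 + 1.282)² × (11.3/3.0)² gives 299 per arm, or 300 with the t distribution, and 300/0.6 = 500, as SAP 3.4 states. For the CACE set, SAP 6.9 gives Groups 1 and 4 plus replenishment: 446 + 238 + 1457 = 2141. Then 2141 × 0.7/3 × 0.6 is about 300 per arm in PROMOTE.

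**Assumptions.** The documents give no complier rates. The only usage figure is the 20% who never signed in (SAP 6.9), not split by arm. Let pE and pC be the EC and CBT compliance rates, tE and tC the gains from complying, and q the share who would comply with CBT but not EC. Use below the threshold is taken to have no effect. Gains are set at tE = 5 and tC = 3 for illustration.

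**Formulas.**

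- SAP 6.6 target (EC minus CBT among EC compliers): tE − tC(pC − q)/pE
- EC-app coding: (pE·tE − pC·tC)/pE
- Shift of EC-app coding from the target: −q·tC/pE, with q at least pC − pE
- Three-arm model (two exposures, two arm indicators as instruments, EC versus CBT as a difference): tE − tC

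| EC/CBT compliance | q | Target | EC-app coding | Three-arm |
|---|---|---|---|---|
| 30/40% | 10% | 2.00 | 1.00 | 2.00 |
| 35/40% | 5% | 2.00 | 1.57 | 2.00 |
| 40/40% | 0 | 2.00 | 2.00 | 2.00 |
| 40/40% | 5% | 2.38 | 2.00 | 2.00 |
| 40/35% | 0 | 2.38 | 2.38 | 2.00 |
| 40/30% | 0 | 2.75 | 2.75 | 2.00 |

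Each row uses the smallest possible q, except the fourth. At 30/40%: EC-app coding (0.3×5 − 0.4×3)/0.3 = 1.0; target 5 − 3×0.3/0.3 = 2.0. At 40/30%: EC-app coding (0.4×5 − 0.3×3)/0.4 = 2.75; target 5 − 3×0.3/0.4 = 2.75. A simulation of 2,000,000 participants at 30/40%, with both gains equal to 3, gave −0.99 against a true value of 0. The formula gives −1.0.

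**Which model is better?** Neither is in general. EC-app coding is exact when q = 0. The three-arm model matches the SAP's target when pC − q = pE, that is, when every EC complier would also comply with CBT. Otherwise it misses, by 0.75 at 40/30% even with homogeneous gains. At 40/40% with q = 5%, both miss by 0.38.

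**Additivity.** At 40/30% with q = 0, the true complier effects are 5 (EC versus usual care), 3 (CBT versus usual care) and 2.75 (EC versus CBT among EC compliers). Since 5 − 3 = 2, the true values do not add. The cells refer to different complier groups, so failure to add is not evidence of error.

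**Precision.** With 300 per arm and 30% EC compliance, the approximate standard error under EC-app coding is SD × √(2/300)/0.3. That is 1.6 at SD 6.0 and 3.1 at SD 11.3, the range quoted in Protocol 10.1.1. Both exceed the 1.0-point shift.

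**Single-flag coding at 30/40%.** First-stage F is 0.1²/[(0.21 + 0.24)/300] = 6.7, and the standard error is 11.3 × √(2/300)/0.1 = 9.2. The weakness would be plain from the first stage, and the coding does not fit the stated target, since complying with CBT is not complying with EC.

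**The case for a change.** The strongest case for amending rests on the algebra, which is right. If CBT works, use of EC below the threshold does nothing, and more people comply with CBT than with EC, at least pC − pE of participants break the assumption. Two equally effective apps (gains of 3 each) at 30/40% would then show an EC deficit of (0.9 − 1.2)/0.3 = −1.0. SAP 6.6 itself anticipates differential adherence. Under SAP 7.1 the analyses beyond the masked 3-month intention-to-treat set follow the unmasking, so the exposure could be settled after allocations are known. One sentence would close the gap at no cost in data.

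The omission, the formula and the late choice all stand. Four things limit them.

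- The plan adopts no faulty coding. Its target points to EC-app compliance, while its global p-value column fits a joint three-arm model at least as well.
- Nothing in the documents says that CBT compliance will exceed EC compliance. Protocol section 8 describes matched delivery and expects similar drop-out to be more likely. That concerns attrition rather than the complier threshold, but it gives no support for a gap in the harmful direction.
- Replacing the coding with the three-arm model would change the estimand, and deleting the cell would give up a planned analysis. Each is a trade-off.
- Adherence below the threshold may still bring benefit, in which case the assumption can hold or fail in ways the simple formula does not capture.

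**Conclusion.** The exposure for EC versus CBT is unnamed, and that is a gap in detail, not an error. Under EC-app coding the shift is −q·tC/pE: zero when q = 0, and at least 1.0 WEMWBS point against EC at an assumed 30/40% with a CBT gain of 3. Its actual size and likelihood cannot be established, because no complier rates are given and the figures assume no effect below the threshold.

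The consequences are contained. CACE is secondary, Protocol 10.6 has the observed-data intention-to-treat results interpreted first, and SAP 5.6 with Table A.2 reports Challenge and Tool use for each active arm, so unequal uptake will be visible. An analyst filling this cell would ordinarily state the exposure and its assumption beside the estimate. The evident alternatives do no better against the SAP's own target across the plausible range, so no change to the plan is needed.
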